6.5.4. Consumption

The total annualized rFVIII Fc consumption (IU/kg) will be calculated for each subject using the following formula:

$$\text{Annualized consumption} = \frac{\text{Total IU/kg of study drug received during the efficacy period}}{\text{Total number of days during the efficacy period}} \times 365.25$$

The total amount of rFVIII Fc received will be the sum of the nominal IU/kg administered for each injection based on the units of rFVIII Fc as recorded from the subject's diary and eCRF and his most recent weight.

Total annualized rFVIII Fc consumption will be determined for each treatment regimen during the efficacy period (i.e., excluding surgery/rehabilitation periods [major and minor surgeries]).

For personalized prophylaxis regimen, additional injections administered will be included in the consumption calculations.

Consumption is a secondary endpoint in this study. A description of how consumption will be summarized is provided in Section 7.3.3.

6.5.5. Compliance

Prophylactic dose compliance will assess adherence to the Investigator's recommendations for dosing. Prophylactic dose compliance will be assessed during the efficacy period.

The prophylactic dose compliance rate will be summarized for overall prophylaxis regimen for the FAS. See Section 6.5.5.2 for further details on prophylactic dose compliance.

Except for doses administered in the clinic, study treatment may be administered by a caregiver or self-administered by the older children in the study.

Data from the eCRF and EPD will be considered for the analysis of treatment received and subjects' compliance with the study protocol; compliance has been defined by the Sponsor. Compliance with prestudy FVIII will not be a considered measurement for this study.

6.5.5.1. Compliance in the Treatment of Bleeding Episodes

Bleeding episodes are defined in Section 7.1.1. All bleeding episodes during the efficacy period for which there is a date and time for both the onset of the bleed and treatment of the bleed will be evaluated for compliance. Compliance will first be determined on a per-bleed basis and then on a per-subject basis. That is, compliance for each bleeding episode will be determined and then the overall percentage of bleeding episodes for which treatment was in compliance will be determined for each subject.

The definition of compliance for the treatment of an individual bleeding episode, as specified by the Sponsor, is no more than 8 hours between the onset of the bleed and the initiation of treatment for the bleed. Thus, the compliance rate for the treatment of bleeding episodes will be measured by determining the proportion of injections administered within a maximum of 8 hours of the initial sign of a bleed, as follows:

$$\text{Treatment of bleed compliance rate} = \frac{\text{Number of first injections to treat a bleed taken within 8 hours of the first sign of a bleed}}{\text{Total number of evaluable bleeding episodes}} \times 100$$

The following circumstances result in a bleeding episode being considered not evaluable for the determination of this compliance rate:

- the type of bleed has been classified as Unknown based on the definition of a bleeding episode (>72 hours between consecutive injections) since there is no onset time
- a missing bleed time for a spontaneous or traumatic bleed
- a bleed time that was recorded as being after the time of treatment

Bleeding episodes for which the first injection for treatment was with non-study drug will be included in the evaluation of compliance. Inclusion of bleeding episodes treated with non-study drug is discussed in Section 7.1.1.

Descriptive statistics of the per-subject compliance rate as well as a categorical summary of these data (<80%, ≥80%) will be presented for overall treatment regimen for the FAS.

6.5.5.2. Compliance of Prophylactic Injections

The compliance rate of each subject to the prescribed prophylactic dosing regimen during the efficacy period will be calculated in 2 ways, as dose compliance and as dosing interval compliance. Compliance will first be determined on a per-injection basis and then on a per-subject basis. That is, compliance for an individual dose or dosing interval will be determined and then the overall percentage of doses and dosing intervals that were in compliance will be determined for each subject.

For the purpose of evaluating compliance, the following will be considered per injection:

- the nominal dose taken compared to the nominal dose prescribed
- the actual day of treatment compared to the prescribed day of treatment

An individual dose will be considered compliant if it is within 80% to 125% of the prescribed dose. An individual dosing interval will be considered compliant if the time between two prophylactic doses is within 24 hours of the prescribed dosing interval. Prescribed dose and dosing intervals are according to the Investigator. Instructions provided to the subject by the Investigator regarding dose or dosing interval changes will be used to determine compliance as of the date the information was provided to the subject.

The actual dosing intervals will be calculated as the length of time between consecutive prophylactic doses (date/time of PR_{x+1} – date/time of PR_x). PR_{x+1} and PR_x are also discussed in Section 6.5.3. The actual time between doses will be determined in minutes and converted to days as the number of minutes divided by 1440. The prescribed dosing interval will be taken from the eCRF as recorded by the Investigator. The absolute value of the difference between the actual and prescribed dosing intervals must be ≤1 day (+/- 24 hours) in order to be compliant.

All prophylactic injections will be used to determine prophylactic dose compliance; only the prophylactic injections used to determine the average prophylactic dosing interval (i.e., intervals

not separated by a bleeding episode or surgical/rehabilitation period), as detailed in Section 6.5.3, will be used to evaluate prophylactic interval compliance. Dose and dosing interval compliance rates per subject will be determined as follows:

$$\text{Dose compliance rate} = \frac{\text{Number of doses taken within 80\% to 125\% of prescribed dose}}{\text{Total number of doses}} \times 100$$

where the percentage of a prescribed dose is calculated as: (nominal dose taken/prescribed dose) x100

and the ‘nominal dose taken’ will be determined from the nominal potency labeled on the vials used by the subject for each injection of rFVIII Fc.

$$\text{Dose interval compliance rate} = \frac{\text{Number of doses taken within +/- 24 hours of prescribed day/time}}{\text{Total number of intervals}} \times 100$$

A subject is considered ‘dose compliant’ or ‘dosing interval compliant’ if his respective rate is at least 80%.

Descriptive statistics of the percentage of nominal doses taken per subject within the 80% to 125% range for dosing compliance as well as frequencies for the dose compliance rate (<80%, ≥80%) will be presented for overall prophylaxis regimen for the FAS. Similarly, descriptive statistics of the percentage of doses taken per subject within ±24 hours of the prescribed day as well as frequencies of the dosing interval compliance rate (<80%, ≥80%) will be presented for the FAS.

Based on their per-subject compliance rates for dose and dosing interval (each <80%, ≥80%), subjects will be further classified into the following mutually exclusive categories for overall compliance to their prophylactic treatment as:

- Both dose and interval compliant
- Dose compliant or interval compliant (but not both)
- Neither dose nor interval compliant

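### SAP 6.5.5.2 scores prophylaxis compliance only on doses and intervals that occurred, so runs of missed doses are under-counted and, in extreme patterns, a subject taking under half his doses passes on both rates

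*SAP*

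**What the plan says.** SAP 6.5.5 gives the purpose: "Prophylactic dose compliance will assess adherence to the Investigator's recommendations for dosing". It restricts the assessment to the efficacy period. SAP 6.5.5.2 then defines two rates.

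- **Dose rate.** "An individual dose will be considered compliant if it is within 80% to 125% of the prescribed dose". The doses that enter are those given: "All prophylactic injections will be used to determine prophylactic dose compliance". The denominator is labelled only as the total number of doses.
- **Interval rate.** "An individual dosing interval will be considered compliant if the time between two prophylactic doses is within 24 hours of the prescribed dosing interval". "The actual dosing intervals will be calculated as the length of time between consecutive prophylactic doses", and "The absolute value of the difference between the actual and prescribed dosing intervals must be ≤1 day (+/- 24 hours) in order to be compliant". The denominator is the total number of intervals. Only intervals "not separated by a bleeding episode or surgical/rehabilitation period" are used.

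A subject passes on each rate at 80% or more. The best of the three overall classes is "Both dose and interval compliant".

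Two rules elsewhere matter. SAP 6.5.3 stops an interval at the prophylactic dose before a bleed and resumes at the first one after it. SAP 5.3.2 cuts gaps of more than 28 days between injections out of the efficacy period for prophylactic regimens, on the footing that they result from missing data.

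**The concern.** The stated aim is adherence to what the investigator prescribed, yet the number of doses prescribed appears in neither denominator. A skipped dose cannot lower the dose rate. A run of skipped doses stretches one interval, which fails once however many doses it should have contained. If a bleed falls in that interval, or it exceeds 28 days, it does not count at all. A steady delay of up to one day per dose passes in full.

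The rates are therefore most flattering for subjects with long or repeated lapses. What is at stake is the meaning of the compliance table: a high figure would not by itself show that the prescribed number of doses was taken.

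**Working it through.** The SAP gives no expected compliance figure, so there is nothing to reproduce. I applied its two formulas to illustrative dosing patterns.

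**Inputs.** The ±1 day window and 80% pass mark are from SAP 6.5.5.2. The 28-day cut is from 5.3.2. The prescribed intervals are from 3.2.1.2: every 3 to 5 days, twice weekly (taken as a 3.5-day average), weekly, and down to every 2 days in pediatric subjects.

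**Assumptions.** Every dose taken is of the prescribed size, so the dose rate is 100%. There are no bleeds or surgery. Each interval is counted as one dose taken, so a fully adherent subject scores 100% on both rates and on doses taken.

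**Formulas.** Let t be the prescribed interval, k the lapse length (28 days or less), c the number of on-time intervals and x the number of lapses.

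- Interval rate = c/(c + x)
- Share of prescribed doses taken = (c + x)·t/(c·t + x·k)

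**Moderate patterns, every 3 days over 365 days** (365/3 = 121.7 doses prescribed):

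- Four 27-day lapses: c = (365 − 108)/3 = 85.7. Interval rate 85.7/89.7 = 95.5%; doses taken 89.7/121.7 = 73.7%.
- Six 27-day lapses: c = (365 − 162)/3 = 67.7. Interval rate 67.7/73.7 = 91.9%; doses taken 73.7/121.7 = 60.5%.

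**At the pass mark.** An 80% interval rate means c = 4x, so the share taken is 5t/(4t + k). For t = 3 this is 15/39 = 38.5% with 27-day lapses and 15/27 = 55.6% with 15-day lapses. With k = 28, the longest gap still counted:

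| Prescribed interval | Other four intervals on time: 5t/(4t + 28) | Other four one day late: 5t/(4(t + 1) + 28) |
|---|---|---|
| 2 days | 27.8% | 25.0% |
| 3 days | 37.5% | 34.1% |
| 3.5 days (twice weekly) | 41.7% | 38.0% |
| 4 days | 45.5% | 41.7% |
| 5 days | 52.1% | 48.1% |
| 7 days | 62.5% | 58.3% |

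**One subject in full.** Every 3 days: four on-time intervals, then one of 21 days (six doses missed). Each cycle lasts 33 days. Eleven cycles last 363 days, with 55 of 121 prescribed doses taken (45.5%). Interval rate 44/55 = 80.0%; dose rate 100%. He falls in the top class.

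**Gaps over 28 days.** These are dropped, so the interval rate becomes 100%. Four on-time intervals then a 30-day gap at every 3 days: 5 of (12 + 30)/3 = 14 doses, 35.7%. Four on-time intervals then a 56-day gap on weekly dosing: 5 of (28 + 56)/7 = 12 doses, 41.7%.

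**Drift.** Every dose one day late gives a 100% interval rate with t/(t + 1) of doses: 75% at every 3 days, 66.7% at every 2 days.

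**Isolated misses.** Four 3-day intervals then one of 6 days: interval rate 80%, doses taken 5/6 = 83.3%. Here the SAP rate is slightly stricter than the share taken.

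**The case against.** **The table has no downstream use.** This stands. The bleeding rate is subset by timeliness of diary entry (SAP 6.5.5.3 and 7.3.1), not by prophylactic compliance. No endpoint or analysis set uses the compliance classes, and the study tests no hypothesis. A reader might infer that the annualized bleeding rates by regimen are validated by this table, or biased through it. The documents do not support either reading.

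**The shortfall shows elsewhere.** This stands in part. Average dosing interval and weekly dose (6.5.3), annualized consumption (6.5.4) and exposure (7.3.2) are all reported. The worked subject would show an average interval of 363/55 = 6.6 days against 3 prescribed. But these outputs do not feed the compliance classes. Average interval, weekly dose and consumption also exclude gaps over 28 days.

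**The extreme patterns are unlikely.** This also stands in part. The 38.5% case needs about 9.4 lapses of 27 days, roughly 253 of 365 days. The documents give no lapse frequency. Bimonthly calls, diary review, vial accountability and discontinuation for noncompliance (Protocol 7.1, 10.4, 12.1.4, 11.1) should catch such subjects. The four-lapse case does not depend on so extreme a pattern.

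**The window is a sponsor choice.** The ±24-hour tolerance is a stated criterion, and scoring by interval suits a schedule that shifts after a late dose. Drift is therefore the weaker part of the point.

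**The denominators might mean doses prescribed.** The SAP does not label them, and it mentions a prescribed day of treatment. But the operative text builds both rates from injections given and the time between them. If prescribed doses were intended, the SAP needs to say so.

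**Conclusion.** The point holds as a limited defect in a descriptive table. Prescribed doses are in neither denominator, so runs of missed doses and steady drift overstate adherence. The size depends on the pattern: 95.5% against about 74% of doses taken for four 27-day lapses in a year at every 3 days, with wider differences as lapses accumulate.

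The top class can hold a subject who took under half his doses, but only with long or repeated lapses. Counting only gaps of 28 days or less, this is reachable at every 2, 3 and 4 days and twice weekly. At every 5 days it also needs the other intervals to run late (48.1%). On weekly dosing the minimum is 58.3%, and under half is reached only when gaps over 28 days are dropped.

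A reader might infer that reported compliance is always inflated. It is not: strictly isolated single misses are scored slightly more severely than the share taken. All figures assume correctly sized doses, no bleeds and no surgery. They show what the rule permits, not how often it would happen.

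**What to change.** In SAP 6.5.5.2 add a third per-subject measure: routine prophylactic doses taken divided by doses expected.

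- Doses expected = prophylaxis days outside surgical/rehabilitation periods, divided by the prescribed interval in force on the eCRF.
- Keep intervals that contain a bleed in the count.
- Do not count additional prevention doses in the numerator, so that they cannot offset missed routine doses.
- Show the ratio with and without gaps over 28 days. The SAP treats those as missing data but has no rule to tell missing records from missed doses.
- Apply the same split at 80% and require it for the class compliant on both. Keep the two present rates as descriptions.

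The worked subject would then score 45.5% and leave the top class.

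The cost is SAP wording and one derived variable from data already collected. There are two downsides. An injection that was given but not recorded counts as missed, which matters given the diary-data problems described in SAP 5.4 and 9. Compliance will also look less favourable for subjects with runs of missed doses or drift.

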6.5.5.3. Compliance of EPD Contemporaneous data entry

Injections must be entered into the EPD within 7 days from the date of the injection. Injections entered outside the 7-day window will be reported as protocol deviations. Descriptive statistics of the percentage of the subjects with fewer than 80% of their total individual EPD records entered within this 7-day window and those with 80% or greater of records that met this criteria will be presented for overall treatment regimen for the FAS.

The analysis of ABR, duration of dosing, and adverse events in safety, as described in Sections 7.3.1, 7.3.2, and 8.2.1 respectively, will be presented by subgroups based upon this percentage.

7. EFFICACY AND PHARMACOKINETIC ANALYSIS

7.1. General Efficacy Principles

Unless specified otherwise, only data occurring during the efficacy period will be used in analyses and summaries relating to bleeding, consumption, and compliance in the treatment of bleeding episodes; efficacy data collected during the surgical/rehabilitation periods (major and minor) will not be included (see Section 5.3.1).

7.1.1. Bleeding Episodes

Bleeding episodes will be recorded in both the EPD and eCRF; this information will be used to derive the secondary efficacy endpoints. During the course of the study the investigator was given the opportunity to disagree with the type of bleed (spontaneous, traumatic) as classified by the subject/caregiver and the subject/caregiver was subsequently given the opportunity to agree or disagree with the reclassification. If the subject/caregiver agreed with the Investigator's assessment, then all analyses subset by type of bleed will be based on the Investigator's determination of the bleed type whether or not the change was made to the subject's records.

A standardized definition of a bleeding episode has been applied to this study, as follows. A bleeding episode starts from the first sign of a bleed, and ends no more than 72 hours after the last treatment for the bleed, within which any symptoms of bleeding at the same location, or injections less than or equal to 72 hours apart, are considered the same bleed. Any injection to treat the bleed taken more than 72 hours after the preceding one will be considered the first injection to treat a new bleed. For the purpose of analysis, the latter injection will be associated with a new bleeding episode and classified as type=Unknown. The location(s) associated with the original bleeding episode will be carried forth to the new bleeding episode; the onset date and time of bleeding will be unknown and hence considered missing. Any bleeding at a different location is considered a separate bleeding episode regardless of the time from the last injection.

This algorithm will also apply when a follow-up injection was recorded subsequent to a prophylactic injection. If the follow-up injection was administered >72 hours after the previous injection to treat a bleeding episode (type=spontaneous, traumatic, follow-up), then the follow-up injection will be classified as a new bleeding episode as described above.

Bleeding at a different location will occur when the general bleeding location is different (e.g., in a joint for the original bleeding episode and subsequently in a muscle) or in a sub-location not initially present if in the same location category (e.g., right elbow for the original bleeding episode and subsequently in the right and left elbows). Conversely, a bleeding episode that originally occurs in the right elbow and left knee and is reported as a new bleed within 72 hours as being only in the right elbow will be considered to be in the same location and hence not counted as a new bleeding episode.

A bleeding episode that occurs in multiple locations will be counted as a single event when determining the overall annualized number of bleeding episodes. However, in summaries by bleeding location, the bleeding episode will be counted in each location for which it is reported with the exception that bleeding that occurs in more than one sub-location of the same location category (e.g., 2 or more different joints) will be counted as just one for that location category.

Only bleeding episodes that were treated with at least one dose of FVIII (whether rFVIII-Fc or a non-study drug) will be included in the analysis of endpoints evaluating bleeding. That is, bleeding episodes that were not treated at all will not be included. Bleeding episodes that were treated with non-study medication will be included in the determination of the annualized bleeding rate. The handling of bleeding episodes treated with non-study FVIII for other endpoints is discussed in Sections 7.4.1.

Bleeding episodes of an unknown type will be included in the determination of the annualized bleeding rate and in summaries based on bleeding episodes but, unless specified otherwise, will not be included in summary tables where endpoints are summarized by type of bleed.

The per-subject annualized number of bleeding episodes, hereafter referred to as the annualized bleeding rate (ABR), will be calculated for each subject using the following formula:

$$\text{ABR} = \frac{\text{Number of bleeding episodes during the efficacy period}}{\text{Total number of days during the efficacy period}} \times 365.25$$

7.1.2. Multiplicity

Multiplicity is not a concern in this study since no statistical tests are being performed on the efficacy endpoints.

7.2. Primary Endpoint

There are no primary efficacy endpoints in this study.

7.3. Secondary Endpoints

7.3.1. Annualized Bleeding Rate

The ABR will be summarized using categorical (e.g. 0, >0-5, >5-10, >10-20, etc.) and descriptive statistics for the FAS. All types of bleeding episodes (spontaneous, traumatic, and type unknown) will be included in determining the annualized number.

As a description of the raw data collected in this study, the unadjusted number of bleeding episodes per subject will be summarized using categorical (e.g. 0, 1-3, 4-6, 7-10, 11-15, etc.) and descriptive statistics over all bleeding episodes and by type of bleed (spontaneous, traumatic, and type unknown). The number and percentage of subjects experiencing a bleeding episode will be summarized categorically for any bleeding episode and for each type of bleed by location (joint, muscle, internal, skin/mucosa, unknown); percentages will be based on each treatment regimen in study 8HA01EXT for FAS. Of note, the number of subjects with a bleeding episode for which the location is unknown will be tabulated in these summaries but no further analysis of unknown bleeding locations is planned. The total subject years followed will be provided in order to put the unadjusted numbers in perspective.

In addition, summaries of the ABR will also be provided for the following subgroups:

- type of bleed (spontaneous, traumatic)
- location of the bleed (joint, muscle, internal, skin/mucosa)
For the purpose of analysis bleeding episodes with a location of iliopsoas will be

treated as a muscle bleed; however, the location will be displayed as iliopsoas in the listings.

- other combinations of type and location of bleed (spontaneous muscle, spontaneous internal, spontaneous skin/mucosa, traumatic joint, traumatic muscle, traumatic internal, traumatic skin/mucosa)
- target joint at screening in the parent study
- contemporaneous entry compliance of \leq 80%, as described in Section 6.5.5.3.

